7.2.2. Exclusion Criteria

A patient who meets any of the following criteria will be excluded from the study:

1. Prior treatment with an agent that blocks the PD-1/PD-L1 pathway.
2. Prior treatment with other systemic immune-modulating agents that was
 - a. less than 4 weeks (28 days) of the enrollment date, or
 - b. associated with imAEs of any grade within 90 days prior to enrollment, or
 - c. associated with toxicity that resulted in discontinuation of the immune-modulating agent.Examples of immune-modulating include therapeutic vaccines, cytokine treatments (other than granulocyte colony stimulating factor, thrombopoietin analogues, or erythropoietin), or agents that target cytotoxic T lymphocyte antigen 4 (CTLA-4), 4-1BB (CD137), PI 3-K-delta, LAG3, or OX-40.
3. Major surgery or radiation therapy within 14 days of first administration of study drug
4. Has received treatment with an approved systemic therapy within 4 weeks of first dose of study drug, or has not yet recovered (ie, grade ≤ 1 or baseline) from any acute toxicities except for laboratory changes as described in inclusion criteria and as below:
 - a. Neuropathy of grade ≤ 2
 - b. Alopecia of any grade
5. Has another malignancy that is progressing or requires active treatment and/or history of malignancy other than cervical cancer within 3 years of date of first planned dose of study drug, except:
 - a. Non-melanoma skin cancer that has undergone potentially curative therapy
 - b. Ductal carcinoma in situ of the breast
 - c. Any tumor that has been deemed to be effectively treated with definitive local control (with or without continued adjuvant hormonal therapy), and the patient is deemed to be in complete remission for at least 2 years prior to first dose of study drug, and no additional therapy is required during the study period.

Note: Patients with hematologic malignancies (eg, chronic lymphocytic leukemia) are excluded.

6. Has any condition that requires ongoing/continuous corticosteroid therapy (>10 mg prednisone/day or anti-inflammatory equivalent) within 4 weeks prior to the first dose of study drug. Patients who require a brief course of steroids (up to 2 days in the week before enrollment) or physiologic replacement are not excluded.
7. Has ongoing or recent (within 5 years) evidence of significant autoimmune disease that required treatment with systemic immunosuppressive treatments. The following are not exclusionary: vitiligo, childhood asthma that has resolved, endocrinopathies (such as hypothyroidism or type 1 diabetes) that require only hormone replacement, or psoriasis that does not require systemic treatment.
8. Has untreated or active primary brain tumor, CNS metastases, leptomeningeal disease or spinal cord compression.

Exception: Patients with previously treated brain metastases may participate provided that the lesions are stable (without evidence of progression between 2 consecutive scans

(eg, CT scan and/or MRI) at least 6 weeks prior to imaging obtained during the screening period), there is no evidence of new or enlarging brain metastases, and the patient does not require any immunosuppressive doses of systemic corticosteroids for management of brain metastases within 4 weeks of the first dose of study drug.

9. Has encephalitis, meningitis, organic brain disease (eg, Parkinson's disease) or uncontrolled seizures in the year prior to first dose of study drug.
10. Has a known history of, or any evidence of interstitial lung disease, or active, non-infectious pneumonitis within 5 years prior to the first dose of study drug. A history of radiation pneumonitis in the radiation field is permitted.
11. Has participated in a study of an investigational agent or an investigational device within 4 weeks of first dose of study drug.
12. Has uncontrolled infection with human immunodeficiency virus (HIV), hepatitis B or hepatitis C infection; or diagnosis of immunodeficiency.

NOTES:

- Patients will be tested for hepatitis C virus (HCV) and hepatitis B virus (HBV) at screening.
- Patients with known HIV infection who have controlled infection (undetectable viral load (HIV RNA PCR) and CD4 count above 350 either spontaneously or on a stable antiviral regimen) are permitted. For patients with controlled HIV infection, monitoring will be performed per local standards.
- Patients with hepatitis B (HepBsAg+) who have controlled infection (serum hepatitis B virus DNA PCR that is below the limit of detection AND receiving anti-viral therapy for hepatitis B) are permitted. Patients with controlled infections must undergo periodic monitoring of HBV DNA. Patients must remain on anti-viral therapy for at least 6 months beyond the last dose of investigational study drug.
- Patients who are hepatitis C antibody positive (HCV Ab+) who have controlled infection (undetectable HCV RNA by PCR either spontaneously or in response to a successful prior course of anti-HCV therapy) are permitted.

13. Has any infection requiring hospitalization or treatment with IV anti-infectives within 2 weeks of first dose of study drug.
14. Has received a live vaccine within 4 weeks of planned start of study medication.
15. Has had prior allogeneic stem cell transplantation, or autologous stem cell transplantation within 12 weeks of the start of study drug, unless discussed with and approved by the sponsor.
16. Recipients of organ transplants at any time unless discussed with and approved by the medical monitor.
17. Has known allergy or hypersensitivity to components of study drug
18. Has known psychiatric or substance abuse disorders that would interfere with participation with the requirements of the study.

19. Has any medical condition, co-morbidity, physical examination finding, or metabolic dysfunction, or clinical laboratory abnormality that, in the opinion of the investigator, renders the patient unsuitable for participation in a clinical trial due to high safety risks and/or potential to affect interpretation of results of the study
20. Member of the clinical site study team or his/her immediate family, unless prior approval granted by the sponsor.
21. Patients with a positive serum/urine hCG pregnancy test must have pregnancy medically ruled out to be eligible for study. Breastfeeding women are also excluded.
22. Continued sexual activity in women of childbearing potential (WOCBP)*, or sexually active men, who are unwilling to practice highly effective contraception prior to the initial dose/start of the first treatment, during the study, and for at least 6 months after the last dose. Highly effective contraceptive measures include:
 - a. stable use of combined (estrogen and progestogen containing) hormonal contraception (oral, intravaginal, transdermal) or progestogen-only hormonal contraception (oral, injectable, implantable) associated with inhibition of ovulation initiated 2 or more menstrual cycles prior to screening
 - b. intrauterine device (IUD); intrauterine hormone releasing system (IUS);
 - c. bilateral tubal ligation
 - d. vasectomized partner (provided that the male vasectomized partner is the sole sexual partner of the WOCBP study participant and that the vasectomized partner has obtained medical assessment of surgical success for the procedure)
 - e. and/or sexual abstinence^{†‡}.

* WOCBP are defined as women who are fertile following menarche until becoming postmenopausal, unless permanently sterile. Permanent sterilization methods include hysterectomy, bilateral salpingectomy, and bilateral oophorectomy.

A postmenopausal state is defined as no menses for 12 months without an alternative medical cause. A high follicle stimulating hormone (FSH) level in the postmenopausal range may be used to confirm a postmenopausal state in women not using hormonal contraception or hormonal replacement therapy. However, in the absence of 12 months of amenorrhea, a single FSH measurement is insufficient to determine the occurrence of a postmenopausal state. The above definitions are according to Clinical Trial Facilitation Group (CTFG) guidance. Pregnancy testing and contraception are not required for women with documented hysterectomy or tubal ligation.

† Sexual abstinence is considered a highly effective method only if defined as refraining from heterosexual intercourse during the entire period of risk associated with the study drugs. The reliability of sexual abstinence needs to be evaluated in relation to the duration of the clinical trial and the preferred and usual lifestyle of the patient.

‡ Periodic abstinence (calendar, symptothermal, post-ovulation methods), withdrawal (coitus interruptus), spermicides only, and lactational amenorrhoea method (LAM) are not acceptable methods of contraception. Female condom and male condom should not be used together.

7.3. Premature Withdrawal from the Study

A patient has the right to withdraw from the study at any time, for any reason, and without repercussion.

The investigator and sponsor have the right to discontinue a patient from study treatment or withdraw a patient from the study at any time.

Reasons for discontinuation of study treatment or withdrawal from the study may include, but are not limited to:

- Patient withdrawal of consent at any time
- Any medical condition that the investigator or sponsor determines may jeopardize the patient's safety if he or she continues in the study or continues treatment with study drug
- The investigator or sponsor determines it is in the best interest of the patient
- Patient noncompliance (eg, not complying with protocol required visits, assessments, and dosing instructions)
- Pregnancy.

Every effort should be made to obtain information on patients who discontinue study treatment but who do not withdraw consent to continue participation in the study by completing study assessments, as described in Section 9.1.4.

Rules for discontinuation of study treatment (permanent or temporary) are discussed in Section 8.2.2.

7.4. Replacement of Patients

Patients prematurely discontinued from the study who had received at least 1 treatment with cemiplimab and/or ISA101b will not be replaced (Section 7.3).

8. STUDY TREATMENTS

8.1. Investigational and Reference Treatments

ISA101b is an investigational treatment. Cemiplimab is being used as an investigational treatment for cervical cancer and is approved for the treatment for advanced cutaneous squamous cell cancer (CSCC), locally advanced basal cell carcinoma, and as a first-line treatment option in advanced non-small cell lung cancer.

Additional information regarding cemiplimab and ISA101b is provided in the respective Investigator's Brochures.

8.1.1. Cemiplimab

Cemiplimab (REGN2810) is supplied as a liquid in sterile, single use vials. Cemiplimab will be administered IV at a dose of 350 mg over 30 minutes (\pm 10 minutes) Q3W.

8.1.2. ISA101b

The study drug product ISA101b is provided in 2 vials, HPV-DP-5P containing 5 peptides and HPV-DP-7P containing 7 peptides. Bulk preparation, sterile filtration, filling, and lyophilization have been developed for each drug product. ISA101b 100 μ g/peptide will be administered by SC injections. ISA101b is not provided or prepared as an individual product. Two discrete injections, one of HPV-DP-5P and one of HPV-DP-7P, together *in vivo* constitute ISA101b.

Instructions on dose preparation are provided in the pharmacy manual.

8.2. Dose Modification and Study Treatment Discontinuation Rules

8.2.1. Dose Modification

Dose modification of cemiplimab for an individual patient is not allowed.

If cemiplimab is delayed, interrupted, or discontinued due to toxicity clearly related to cemiplimab as described in the cemiplimab Investigator's Brochure, and this toxicity is not considered related to ISA101b, the remaining doses of ISA101b may be administered. It is recommended to discuss such cases with the Medical Monitor.

If ISA101b is delayed, interrupted, or discontinued due to toxicity clearly related to ISA101b as described in the ISA101b Investigator's Brochure, and this toxicity is not considered related to cemiplimab, the remaining doses of cemiplimab may be administered. It is recommended to discuss such cases with the Medical Monitor.

There will be no dose reduction for ISA101b in this study.

8.2.2. Study Drug Discontinuation

Patients who permanently discontinue from study drug due to disease progression, toxicity, or another reason who do not withdraw consent from study participation will be asked to return to the clinic for all remaining study visits per the visit schedule ([Table 2](#)) and will be expected to continue with safety follow-up assessments.

8.2.2.1. Reasons for Permanent Discontinuation of Study Drug

Study drug (cemiplimab and/or ISA101b) will be permanently stopped in the event of:

- Serious or severe allergic reactions considered related to study drug
- Grade 3 infusion related reaction
- Grade 3 uveitis
- Grade 3 or 4 neurologic toxicity
- Grade 3 or 4 myocarditis/pericarditis
- Any grade 4 non-hematologic toxicity except for clinically insignificant laboratory abnormalities
- Any non-hematologic toxicity that led to temporary withholding of study treatment which does not resolve to grade 1 or baseline within 12 weeks of last study drug infusion except for immune-mediated endocrinopathies controlled with hormonal therapy
- Grade 4 hematologic toxicity that does not resolve to less than grade 4 within 2 weeks of last infusion or to grade 2 (neutropenia) or grade 1 or baseline (others) within 12 weeks of last study drug infusion.
- Physician/patient decision
- Treatment delay of ≥ 84 consecutive days from last dose of study drug

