8.3.1.3.1. Management of ISA101b-Specific Adverse Events

ISA101b will be discontinued for any severe (\geq grade 3) ISR. Severity will be graded according to Section [10.2.5](#).

ISA101b administration should be delayed for the following:

- Any \geq grade 3 ISA101b-related AE.
- Temperature $>38^{\circ}\text{C}$ over the last 24 hours prior to administration.
- Any AE, laboratory abnormality, or intercurrent illness which, in the judgment of the investigator, warrants delaying the dose of ISA101b.

The occurrence of an ISA101b -associated systemic allergic reaction will be managed according to standard practice, including close observation, antihistamines, and fluids, as well as steroids or epinephrine if clinically indicated. ISA101b should not be administered again following resolution of a grade 4 systemic allergic reaction. Refer to the ISA101b Investigator's Brochure for details.

Local ISR at site(s) of previous administration of ISA101b of > grade 3 should be treated symptomatically and followed until resolution to grade 1 is observed.

Patients may resume treatment with the next dose of ISA101b when study drug-related AEs resolve to grade ≤ 1 or baseline value, with the following exception: patients may resume treatment in the presence of grade 2 fatigue.

If day 29 of ISA101b is missed, the second dose of ISA101b will be given on day 45 (± 3 days) and the third dose will be given on day 66 (± 3 days). If day 29 was missed due to an AE or lab abnormality, this must have resolved prior to resumption of dosing.

If day 50 of ISA101b is missed, the third dose of ISA101b will be given on day 66 (± 3 days). If day 50 was missed due to an AE or lab abnormality, this must have resolved prior to resumption of dosing.

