APPENDIX 2. GUIDELINES FOR MANAGEMENT OF IMMUNE-MEDIATED ADVERSE EVENTS

Select immune-mediated adverse events (imAEs) and their management are described in this appendix. Additionally, the following general principles apply to management of imAEs, if not described in detail in this appendix:

Grade 1: Continue study treatment with close monitoring and provide symptomatic management.

Grade 2: Consider withholding study treatment

Grade 3: Withhold study treatment

Grade 4: Discontinue study treatment.

Temporary hold and resumption. Except as described for select imAEs, if cemiplimab is withheld for grade ≤ 3 imAE, consider resuming when the imAE improves to grade 0 or 1 after corticosteroid taper to \leq prednisone 10 mg/day or equivalent.

Permanent discontinuation. Except as described for select imAEs, give an initial dose of 1 to 2 mg/kg/day prednisone or equivalent followed by a taper and permanently discontinue study treatment for:

- Grade 4 adverse reactions (excluding endocrinopathies)
- Recurrent Grade 3 imAEs
- Grade 2 or 3 imAEs persistent for ≥ 12 weeks after the last study treatment
- Requirement for ≥ 10 mg per day prednisone or equivalent lasting ≥ 12 weeks after the last study treatment.

For guidance in addition to that provided here, please refer to regional imAE management guidelines, such as those provided by NCCN or ESMO. In countries where cemiplimab has a marketing authorization the local product information may be consulted. Note that local and regional treatment guidelines and cemiplimab product information may be updated periodically and the latest version should always be reviewed.

Recommended Adverse Event Management for Colitis/Diarrhea

CTCAE v5.0 Grade	Study Treatment Management	Action & Supportive Care Guidelines	Diagnostic Considerations

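### Protocol 8.2.2.1 permanently stops ISA101b after a severe related allergic reaction, while 8.3.1.3.1 permits re-dosing unless the reaction was grade 4; the grade 4 stop also omits Appendix 2's endocrinopathy exception

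*Protocol*

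**What the plan says.** **Allergic reactions.** Section 8.2.2.1 is mandatory and names both drugs. Its first reason for a permanent stop is "Serious or severe allergic reactions considered related to study drug".

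Section 8.3.1.3.1 sets the vaccine-specific rules:

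- Stop for local reactions: "ISA101b will be discontinued for any severe" injection site reaction, with severe defined there as grade 3 or higher.
- Delay list: its first item is any event at or above "grade 3 ISA101b-related AE".
- Bar on re-dosing after a systemic allergic reaction: "ISA101b should not be administered again following resolution of a grade 4 systemic allergic reaction". The reader is then sent to the ISA101b Investigator's Brochure for details.
- Resumption: "Patients may resume treatment with the next dose of ISA101b when study drug-related AEs resolve to grade" 1 or lower, or to baseline.
- Catch-up dates: "If day 29 of ISA101b is missed, the second dose of ISA101b will be given on day 45", with the third dose on day 66. A missed day 50 dose also moves to day 66. An adverse event that caused the miss must first have resolved.

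**Grade 4 toxicity.** Section 8.2.2.1 also stops treatment permanently for "Any grade 4 non-hematologic toxicity except for clinically insignificant laboratory abnormalities". It has an endocrinopathy exception, but only on the separate bullet about toxicity unresolved at 12 weeks. The permanent-stop list in Appendix 2 begins "Grade 4 adverse reactions (excluding endocrinopathies". Its tables for thyroid, pituitary/adrenal and diabetic events say to withhold treatment at grade 4 until the event improves or is clinically stable.

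**The concern.** Section 1.3.3 describes systemic allergic reactions as potentially the most serious adverse reactions to the vaccine. A site working from 8.3.1.3.1, the natural place to look after a vaccine reaction, could give another dose to a patient for whom 8.2.2.1 requires a permanent stop. The section is also lopsided within itself: a grade 3 local reaction ends vaccination, but nothing there ends it after a grade 3 systemic reaction.

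For endocrinopathy the error runs the other way. A site following 8.2.2.1 alone would end cemiplimab for good in a patient whom Appendix 2 would let resume.

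Dosing is interrupted at onset under either rule in both cases; only later resumption differs.

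**Working it through.** The plan has no figure to reproduce. The check is a comparison of texts, followed by a rough count.

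**Step 1: does severe mean grade 3?** Section 8.2.2.1 gives no grade for allergic reactions. The scale in 10.2.5 for events not listed in CTCAE labels grade 3 as severe, and 8.3.1.3.1 defines severe as grade 3 or higher for injection site reactions. Both point the same way.

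**Step 2: the rules side by side.**

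| Event | 8.2.2.1 | Other section | Result |
|---|---|---|---|
| Related systemic allergic reaction to ISA101b, grade 4 | Permanent stop | 8.3.1.3.1: no further ISA101b | Consistent |
| Same, grade 3 | Permanent stop | 8.3.1.3.1: delay, may resume after recovery | Conflict |
| Same, serious but below grade 3 | Permanent stop | 8.3.1.3.1: no specific rule, general resume rule only | Gap |
| Immune-mediated endocrinopathy, grade 4 | Permanent stop | Appendix 2: withhold, resume when improved or stable | Conflict |

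**Step 3: does any clause set precedence?**

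- 8.2.2.2 points to 8.2.3, Appendix 2 and 8.3 for temporary stops. It does not say that they override 8.2.2.1.
- 8.2.3.2 yields to Appendix 2 for its own grade-based principles only.
- 8.2.4 yields to the more detailed sections for its own guidance only.

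None reaches 8.2.2.1. The last two suggest that Appendix 2 was meant to win on endocrinopathy. Nothing comparable exists for the allergic-reaction conflict.

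**Step 4: how many patients?** Section 1.3.3 gives a rate below 5% for systemic allergic reactions at 100 µg/peptide with ISA101, the predecessor product. At 5%, the expected count is 105 × 0.05 = 5.25 patients with a reaction of any grade. That is not a cap: at a true rate of 5%, the chance of six or more is 43%. The grade 3 or serious share is not given.

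Only a reaction after dose 1 or dose 2 leaves a vaccine dose to give. Let p be the rate of grade 3 or serious related reactions, s the share occurring after dose 1 or 2, and q = p × s. Both p and s are assumptions; an even spread over three doses gives s = 2/3. Then:

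- expected patients = 105 × q
- chance of at least one = 1 − (1 − q)^105

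For p = 1% and s = 2/3: q = 0.01 × 2/3 = 0.00667, expected 105 × 0.00667 = 0.70, and chance 1 − 0.99333^105 = 0.505.

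| p | s = 1/3 | s = 2/3 | s = 1 |
|---|---|---|---|
| 0.5% | 16% | 30% (expected 0.35) | 41% |
| 1% | 30% | 50% (expected 0.70) | 65% |
| 2% | 50% | 76% (expected 1.40) | 88% |

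These are chances that a patient arises on whom the two sections disagree. They are not chances of re-dosing, which also needs recovery to grade 1 or baseline and an investigator who chooses to resume. No rate is given for grade 4 endocrinopathy, so that count is unknown.

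**The case against.** The best defence is that a mandatory rule meets a permissive one. Section 8.2.2.1 orders a stop and 8.3.1.3.1 only allows resumption, so a site that stops breaches neither. That is true. But a site that resumes complies with 8.3.1.3.1 and breaches 8.2.2.1, and the protocol does not warn it.

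Second, the delay list need not displace permanent stops. It also takes in grade 3 or higher injection site reactions and grade 4 events, both of which are stopped elsewhere. This stands: the list reads as a minimum action. The problem comes from the grade-specific bar set beside it, which invites the reading that grade 3 systemic reactions fall under the resume rule.

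Third, the grade 4 sentence proves little about intent. It is redundant in any case, because 8.2.2.1 already stops grade 4 non-hematologic toxicity, and this protocol repeats stop rules freely. This also stands, and the conclusion does not rely on inferred intent.

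Fourth, the Investigator's Brochure may settle the matter. It is not among the documents, so this cannot be excluded. The protocol would still contradict itself.

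Fifth, other safeguards exist: four hours of observation after each vaccine dose, reporting of serious events within 24 hours, planned gaps of 28 days (29 − 1) and 21 days (50 − 29) between doses, and a recommendation in 8.2.1 to discuss toxicity delays with the Medical Monitor. They lower the risk without saying which rule applies. The 24-hour rule for events of special interest in 10.1.3 is headed as applying to cemiplimab only, so it may miss a non-serious grade 3 vaccine reaction.

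**Conclusion.** The contradiction is real and should be corrected. For a related grade 3 systemic allergic reaction to ISA101b, 8.2.2.1 requires a permanent stop and 8.3.1.3.1 permits another dose. This rests on reading severe as grade 3, which the protocol's own usage supports. The grade 4 endocrinopathy mismatch is a lesser drafting gap, since the surrounding clauses suggest that Appendix 2 was meant to govern.

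The number affected is small: with two-thirds of reactions leaving a dose to give, 0.35 to 1.4 patients are expected at assumed rates of 0.5% to 2%. The point matters because of the nature of the event, not its frequency. The ORR estimate, its interval and the sample size do not change.

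**What to change.** Make three edits:

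1. In 8.3.1.3.1, replace the grade 4 sentence with: *No further ISA101b may be given after any systemic allergic reaction related to ISA101b that is serious or of grade 3 or higher.*
2. In 8.3.1.3.1, add: *The delay, resume and missed-dose rules do not apply to events that require permanent discontinuation under Section 8.2.2.1 or this section.*
3. In 8.2.2.1, extend the bullet "Any grade 4 non-hematologic toxicity except for clinically insignificant laboratory abnormalities" with: *and immune-mediated endocrinopathies managed per Appendix 2.*

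Edit 2 alone would settle precedence. Edit 1 is still worth making, because a sentence naming grade 4 alone will keep misleading readers. The opposite repair, relaxing 8.2.2.1 to grade 4, would also remove the contradiction. It fits the protocol less well: grade 3 or higher infusion reactions to cemiplimab, which 8.3.1 says may also be called systemic hypersensitivity reactions, already end treatment.

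The edits change stopping rules, so they need an IRB/EC-approved amendment (Sections 13.4 and 14) and can be bundled with the next one. A few patients would lose vaccine doses: two after a dose 1 reaction, one after dose 2. Cemiplimab may continue under 8.2.1 where the reaction is clearly due to ISA101b. Sample size, visit schedule and data collection are unchanged.

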8.2.4. General Guidance for Management of Adverse Events

This subsection provides general guidance of treatment-related AEs ([Table 1](#)) that are not specifically addressed in guidelines for management of imAEs (Section [8.2.3.2](#) or [Appendix 2](#)) or in management of acute infusion reactions (Section [8.3](#)). In the event of discrepancy between this section and a section that provides for detailed guidance (ie, Section [8.2.3.2](#), [Appendix 2](#) or Section [8.3](#)), the section that provides the more detailed guidance will supersede the general guidance in this section.

Table 1: General Guidelines for Management of Treatment-Related Adverse Events

Toxicity	Grade	Hold Treatment	Restarting Criteria
Hematological Toxicity (other than grade 3 thrombocytopenia greater than 7 days or associated with bleeding, or Grade 4 thrombocytopenia.)	1, 2, 3	No	N/A
	4	Yes	Toxicity resolves to grade ≤ 1 or baseline
Grade 3 thrombocytopenia greater than 7 days or associated with bleeding	3	Yes	Toxicity resolves to grade ≤ 1 or baseline

Toxicity	Grade	Hold Treatment	Restarting Criteria
Grade 4 thrombocytopenia	4	Yes	Discontinue permanently
Nonhematological Toxicity	1	No	N/A
Note: Exceptions to be treated as for Grade 1 toxicity:	2	Consider withholding for persistent symptoms	Toxicity resolves to grade ≤ 1

 Grade 2 alopecia Grade 2 fatigue Clinically insignificant lab abnormality not meeting criteria 	3	Yes	Toxicity resolves to grade ≤ 1
	4	Discontinue permanently	Discontinue permanently

N/A = not applicable

Treatment after an AE may resume at the discretion of the investigator if it is in accordance with the toxicity management guidelines in this protocol, if resumption of treatment is thought to be in the best interest of the patient and if either of the following conditions are met:

- After resolution of an AE to \leq grade 1 (or baseline)
- The AE is considered to be manageable through supportive/medical therapy (eg, grade 3 hypertension that can be controlled with the addition of a second anti-hypertensive agent).

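### Treatment-related grade 4 thrombocytopenia is an unconditional permanent stop in Protocol Table 1 but only a conditional one in 8.2.2.1; the neutropenia recovery grade is also misaligned

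*Protocol*

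**What the plan says.** Protocol 8.2.2.1 lists the events for which cemiplimab and/or ISA101b will be stopped permanently. Its hematologic entry has two limbs. The first is "Grade 4 hematologic toxicity that does not resolve to less than grade 4 within 2 weeks of last infusion". The second continues "or to grade 2 (neutropenia) or grade 1 or baseline (others) within 12 weeks of last study drug infusion". The entry makes no exception for thrombocytopenia, which therefore belongs with the toxicities other than neutropenia. The same list ends with a delay rule: a gap of 84 or more consecutive days since the last dose is itself a permanent stop.

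Protocol 8.2.4 describes its own scope: "This subsection provides general guidance of treatment-related AEs", where these are not specifically covered by the immune-mediated adverse event (imAE) or infusion-reaction guidance. In Table 1, the general hematologic row holds treatment at grade 4 and sets the restart criterion as "Toxicity resolves to grade ≤ 1 or baseline". Grade 4 thrombocytopenia is taken out of that row and given its own: "Grade 4 thrombocytopenia 4 Yes Discontinue permanently".

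The tie-break in 8.2.4 says that, on a discrepancy, "the section that provides the more detailed guidance will supersede the general guidance in this section". The sections it lists are 8.2.3.2, Appendix 2 and 8.3. Section 8.2.2.1 is not among them.

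**The concern.** Both sections govern whether a patient may be treated again after grade 4 thrombocytopenia, and they give different answers for a patient who recovers. Two sites could each follow the text in front of them and handle the same patient in opposite ways on a safety stop.

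The choice also reaches reported results: TEAEs leading to permanent treatment discontinuation (SAP 5.8.1), reasons for treatment discontinuation (SAP 5.4), and exposure and dose intensity (SAP 5.6.2). If sites read different sections, those summaries would mix two rules.

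**Working it through.** No sample size, error rate or event count is involved, so the check sets the two rules side by side, case by case.

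| Case | 8.2.2.1 hematologic entry | Table 1, 8.2.4 | Result |
|---|---|---|---|
| A. Treatment-related grade 4 thrombocytopenia, not an imAE; below grade 4 within 2 weeks of last infusion and at grade 1 or baseline within 12 weeks | Neither limb met | Permanent stop | Conflict |
| B. As A, but still grade 4 at 2 weeks | Permanent stop | Permanent stop | Agree |
| C. As A, but not at grade 1 or baseline by 12 weeks | Permanent stop | Permanent stop | Agree |
| D. Grade 4 thrombocytopenia managed as an imAE | Conditional | Gives way to 8.2.3.2, whose general rule for a grade 4 imAE is to discontinue | Outside the Table 1 question |
| E. Grade 4 thrombocytopenia not related to treatment | Conditional | Outside the scope of 8.2.4 | No conflict with Table 1 |
| F. Treatment-related grade 4 neutropenia settling at grade 2, baseline better than grade 2 | Neither limb met, if below grade 4 within 2 weeks and at grade 2 within 12 weeks | Restart criterion not met | Misaligned |
| G. As F, but baseline is grade 2 | Neither limb met | Restart allowed at baseline | Agree |
| H. Other grade 4 hematologic toxicity, such as anemia | Recovery level: grade 1 or baseline | Recovery level: grade 1 or lower, or baseline | Same recovery grade |

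**Case A** is the direct conflict. The time limits in 8.2.2.1 run from the last infusion, not from onset.

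**Case F** is weaker, because the two figures do different jobs: grade 2 is a threshold for stopping permanently, and grade 1 or baseline is a threshold for restarting. Between them the patient stays on hold. The limits then coincide: 12 weeks × 7 days = 84 days, which is the delay rule in 8.2.2.1. Under the Table 1 row, a patient still held at grade 2 is stopped by the delay rule at about the time the 12-week neutropenia limb would have spared her. For such a patient the grade 2 allowance has little or no effect.

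**Does anything else settle it?**
- The precedence sentence does not name 8.2.2.1. Extending it by analogy does not help: 8.2.2.1 is more detailed on time limits and neutropenia, and Table 1 is more detailed on thrombocytopenia.
- Appendix 2 has no hematologic table.
- Section 8.2.2.2, on temporary stops, points to 8.2.3, Appendix 2 and 8.3, not to 8.2.4.
- The closing text of 8.2.4 makes resumption depend on the protocol's own toxicity guidance, which leads back to the same two sections.
- The SAP contains no stopping rule on this point.

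The amendment history lists 8.2.4 and Table 1 as new in Amendment 2, and describes the change to 8.2.2.1 as the myocarditis/pericarditis wording. That is consistent with a table added without aligning the existing hematologic entry, but does not prove it.

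**The case against.** The best case against is that 8.2.2.1 is a list of sufficient reasons, not a complete one. It says when drug will be stopped; it does not say that drug may otherwise continue. Section 8.2.3.2 already adds permanent stops that 8.2.2.1 omits, such as recurrent grade 3 imAEs and confirmed severe skin reactions. Table 1 can be read the same way, as one more reason, and a site that stops for grade 4 thrombocytopenia breaches nothing in 8.2.2.1. On that reading only a cross-reference is missing.

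That reading is possible, but it does not clear the conflict. Section 8.2.2.1 is not merely silent on thrombocytopenia; it sets time limits and a recovery level that cover it. If Table 1 governs, that recovery path is void for treatment-related thrombocytopenia, and neither section says so. A site working from 8.2.2.1 alone would not know of the Table 1 row.

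On neutropenia more of the objection stands. The texts do not contradict each other outright, and the delay rule closes the gap. The end of 8.2.4 also lets the investigator resume treatment when an event is manageable with supportive therapy, provided this accords with the protocol's toxicity guidance. How that fits with the Table 1 restart criterion is unclear, so the mismatch is secondary.

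A reader might infer that recovery grades differ for all other grade 4 hematologic toxicity. They do not: apart from neutropenia they match (case H). A reader might also infer that every patient with grade 4 thrombocytopenia, or every patient whose neutropenia recovers only to grade 2, is affected. Cases B to E and G show otherwise.

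**Conclusion.** The inconsistency is real and narrow. It concerns treatment-related grade 4 thrombocytopenia, not managed as an imAE, that recovers within the 2-week and 12-week limits of 8.2.2.1: Table 1 stops drug permanently and the 8.2.2.1 hematologic entry does not. The neutropenia mismatch is secondary and limited to patients who settle at grade 2 from a better baseline.

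The documents give no rate for either event, so the number of patients cannot be estimated and may be small. A reader might infer harm to the primary result, but the documents show none: the method for the objective response rate does not depend on which rule applies. The point should be corrected because it is a safety stop that sites could apply differently, and because it feeds the discontinuation and exposure summaries.

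The conclusion assumes that the hematologic entry in 8.2.2.1 is meant to cover thrombocytopenia, as its wording indicates. It takes no view on which rule is clinically right.

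**What to change.** Reconcile Protocol 8.2.2.1 and Table 1 so that grade 4 thrombocytopenia has one rule and grade 4 neutropenia has one rule, stated the same way in both places, and cross-reference the two sections. For neutropenia, say also how the rule works with the 84-day delay rule. The sponsor's clinical team must choose the rules.

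Simply adding 8.2.2.1 to the precedence sentence in 8.2.4 is not a neutral repair: it would tend to let the conditional stop override the unconditional one, and so would settle a clinical question by drafting.

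The cost is protocol wording in a future amendment, with notice to sites. Sample size, data collection and planned analyses do not change.
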